9.2 Discussion of Study Design

The study population consists of subjects who completed Study HZNP-ACT-301; this population was well-defined and consistent with the expected target population for whom ACTIMMUNE will be indicated (pediatric and young adult subjects with a FA functional stage of >1 to <5).

The most common adverse experiences occurring with ACTIMMUNE therapy are FLS or constitutional symptoms such as fever, headache, chills, myalgia, or fatigue that may decrease in severity as treatment continues (see product prescribing information in [Section 17.2](#)). It is hoped that the weekly dose-escalation scheme and the allowable dose adjustments in this study will alleviate the severity of these symptoms. In addition, previous experience with this drug indicates these FLS may be minimized with bedtime administration of ACTIMMUNE and the use of acetaminophen, and/or ibuprofen, and/or diphenhydramine. Therefore, subjects in this study will be instructed to self-administer study drug at bedtime on days when they are not being seen in the clinic for neurological assessments, and the use of acetaminophen, and/or ibuprofen, and/or diphenhydramine (see [Table 9.1](#) for allowable doses) will be allowed throughout the study. On clinic days when neurological assessments are being performed, study drug dosing will occur on site.

The primary efficacy endpoint (change in FARS-mNeuro from Baseline to Week 26) has been agreed upon with the FDA as part of a pre-IND study submission. The measurements used in this study for the primary efficacy endpoint (FARS) are established and well-validated endpoints that have been shown to correlate significantly with functional disability in FA patients [[Friedman et al, 2010](#); [Lynch et al, 2006](#); [Lynch et al, 2005](#)].

In order to maintain the study blind in HZNP-ACT-301, all subjects in this open-label extension study will undergo ACTIMMUNE titration, regardless if they received ACTIMMUNE or placebo in HZNP-ACT-301. The doses planned for dose escalation of ACTIMMUNE in this study are 10, 25, 50, and 100 $\mu\text{g}/\text{m}^2$. The approved dosage of ACTIMMUNE for the treatment of CGD and SMO is 50 $\mu\text{g}/\text{m}^2$ for patients whose BSA is greater than 0.5 m^2 and the highest dose administered in the OLIGA-FA pilot study was also 50 $\mu\text{g}/\text{m}^2$. Although the pilot study showed promising results in the FARS assessment, the lack of clinically meaningful effects on other outcomes indicate a higher dose may be necessary in the treatment of FA. During the ACTIMMUNE development program, the 100 $\mu\text{g}/\text{m}^2$ dose was administered to healthy adult subjects in PK studies, and doses $>100 \mu\text{g}/\text{m}^2$ were administered to subjects with disease states other than the approved indications. As expected, the AE profile of ACTIMMUNE at $>100 \mu\text{g}/\text{m}^2$ in other disease states was broader than that seen among patients with CGD at the 50 $\mu\text{g}/\text{m}^2$ dose. Since the safety profile of the 100 $\mu\text{g}/\text{m}^2$ dose is unknown among pediatric subjects with FA, the study will be monitored by a DSMB, which will advise the Sponsor or its delegate regarding the continuing safety of study subjects and potential subjects as well as the continuing validity and scientific merit of the trial. The decision to modify or halt the study will be made collectively by the CPI, the Sponsor (Horizon), and FARA after review with the FDA.

9.3 Selection of Study Population

9.3.1 Inclusion Criteria

Eligible subjects must meet all of the following criteria:

1. Written informed consent and child assent, if applicable.
2. Completed 26 weeks of blinded treatment in Study HZNP-ACT-301.
3. If female, the subject is not pregnant or lactating or intending to become pregnant during the study, or within 30 days after the last dose of study drug. Female subjects of child-bearing potential must have a negative urine pregnancy test result at Baseline/Day 1 (Week 26 of Study HZNP-ACT-301) and agree to use a reliable method of contraception throughout the study and for 30 days after the last dose of study drug.

9.3.2 Exclusion Criteria

Subjects will be ineligible if, in the opinion of the Investigator, they are unlikely to comply with the study protocol or have a concomitant disease or condition that could interfere with the conduct of the study or potentially put the subject at unacceptable risk.

9.3.3 Removal of Subjects from Therapy or Assessment

All subjects are free to withdraw from study participation at any time, for any reason, and without prejudice to their further medical care. In addition, the investigator may terminate a subject from the study at any time. The primary reason for discontinuation should be recorded on the case report form using one of the following categories:

- Adverse event. The subject experiences an AE that imposes an unacceptable risk to the subject's health, or the subject is unwilling to continue because of an AE.
- Lack of therapeutic effect. The investigator has determined that study drug administration is not benefitting the subject, and continued participation poses an unacceptable risk to the subject.
- Inclusion/exclusion criteria violation. The investigator discovers that the subject did not meet all of the inclusion/exclusion criteria after study enrollment.
- Protocol noncompliance. The subject has a significant protocol deviation, does not comply with study drug administration schedule, or fails to adhere to other study requirements as stated in the protocol.
- Lost to follow-up. The subject does not return to the clinic for scheduled assessments, and does not respond to the site's attempts to contact the subject.
- Voluntary withdrawal. The subject (or subject's legally acceptable representative) wishes to withdraw from the study. The clinical site should attempt to determine the underlying reason for the voluntary withdrawal and document it on the eCRF; if the underlying reason is documented as an AE or lack of efficacy, the category of withdrawal should be marked in the corresponding category and not as voluntary withdrawal.
- Study termination. The Sponsor, DSMB, IRB, or regulatory agency terminates the study.
- Pregnancy.

Following early discontinuation from the study, the subject or his/her legally acceptable representative will be informed regarding the additional study evaluations that are necessary to monitor his/her safety. These subjects or their representatives will be encouraged to complete the PW and Follow-Up Safety Visits.

Discontinued or withdrawn subjects will not be replaced. Subject identification numbers are unique and will not be reassigned.

9.4 Treatments

9.4.1 Treatments Administered

In order to maintain the study blind in HZNP-ACT-301, all subjects in this open-label extension study will undergo ACTIMMUNE titration, regardless if they received ACTIMMUNE or placebo in HZNP-ACT-301.

Subjects will receive SC doses of ACTIMMUNE TIW for 26 weeks. The planned dose escalation consists of two doses of ACTIMMUNE $10 \mu\text{g}/\text{m}^2$, followed by weekly-escalated doses of 25, 50, and $100 \mu\text{g}/\text{m}^2$ TIW on Days 8, 15, and 22, respectively. The first dose of study drug will be administered after the Baseline/Day 1 Visit at home before bedtime according to the subject's TIW dosing schedule.

9.4.1.1 Dose Adjustment Guidelines

The dose of ACTIMMUNE is based on the subject's BSA; therefore, height and weight will be measured at Baseline/Day 1 (Week 26 of Study HZNP-ACT-301) and Weeks 4 and 13, and the dosing volume will be determined using the formula presented in [Section 9.4.7.2](#).

The planned 4-week dose escalation schedule will be implemented if it is tolerated by the subject. If, however, in the opinion of the investigator, the subject experiences severe reactions during dose escalation, the dose will be reduced to the previous dose level, or will be interrupted until the adverse reaction resolves and then restarted at the previous or a lower dose level. Once the previous/lower dose level is tolerated, the dose may then be titrated upwards again to the next dose level as tolerated.

During the dose-escalation period, the clinical site will contact the subjects (or caregivers/legal representatives) via phone calls or email on a weekly basis to monitor AEs and dosing logistics. In addition, subjects may contact the clinical site at any time with dosing or possible drug reaction concerns throughout the study. Dose adjustments may be continued through Week 13, but at Week 13, all subjects should be on a stable tolerated dose and remain at that dose through Week 26. During the stable dosing period, subjects will be contacted by the site via phone calls or emails on a monthly basis to monitor AEs and dosing logistics. Although the dose may not be further increased after Week 13, it may be reduced on a case-by-case basis to manage subsequent drug-related AEs (e.g., elevated liver function tests).

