Patients with FA have frataxin protein levels in peripheral tissues that range from 2-30% of control levels. The level of frataxin protein correlates with age of onset and inversely with the length of the GAA repeat. In carriers, who do not develop symptoms of FA, frataxin protein levels range from 30-80% of control levels [Deutsch et al, 2010]. The lack of symptoms observed in carriers suggests that restoration of frataxin levels in patients to those observed in carriers may lead to substantial improvement of symptoms.

At present, no therapy is approved for use in FA [Corben et al, 2014; Delatycki et al, 2014]. Many of the therapies being developed are designed to increase levels of frataxin, either by reversal of its transcriptional depression or by other means [Arpa et al, 2014; Lynch et al, 2010; Lynch et al, 2012]. Frataxin-depleted cells have an increased sensitivity to oxidative stress. Subtype-selective histone deacetylase (HDAC) inhibition has been successful *in vitro* at increasing levels of transcription of frataxin, and is beginning early stage trials in humans [Rai et al, 2008; Sandi et al, 2011]. Erythropoietin and its derivatives raise frataxin levels in peripheral tissues by non-transcriptional means, but the effect has been too small to observe efficacy in human trials [Boesch et al, 2014; Mariotti et al, 2012].

IFN- γ , a protein produced by the immune system in response to infections, increases both frataxin messenger RNA (mRNA) and protein levels in a variety of different cell types, including cell lines derived from FA patients. In addition, an FA mouse model treated with subcutaneous (SC) injections of IFN- γ for 14 weeks showed improvements in motor coordination, an effect that was mirrored by accumulation of frataxin protein in the DRG tissue in these mice [Tomassini et al, 2012]. Its mechanism of action is as a transcriptional activator of multiple genes. From a therapeutic perspective, IFN- γ 1b (ACTIMMUNE[®]) is approved for use in the US in patients with CGD and SMO (see prescribing information in Section 17.2), and has been investigated in other conditions, including oncology, infectious diseases, and inflammatory disorders.

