In this clinical trial, FA subjects will be dose-escalated weekly (10, 25, 50, and $100 \mu\text{g}/\text{m}^2$ SC TIW). If severe reactions occur during dose escalation, the dosage will be reduced to the previous dose level or therapy will be interrupted until the adverse reaction resolves and then restarted at the previous or lower dose level. By Week 13 of the study, the dose will not be further adjusted and will be maintained for the remainder of the study (an additional 13 weeks of dosing), unless dose reductions are required for drug-related AE management. The dosing of ACTIMMUNE in this protocol is fairly consistent with that already approved for ACTIMMUNE ([Table 7.1](#)). The difference is that in this study, the dose will be titrated to a maximum of $100 \mu\text{g}/\text{m}^2$ compared to the dose of $50 \mu\text{g}/\text{m}^2$ recommended in the current ACTIMMUNE prescribing information ([Section 17.2](#)). Although the pilot study showed promising results in the FARS assessment, the lack of clinically meaningful effects on other outcomes indicate a higher dose may be necessary in the treatment of FA.

Table 7.1 Approved Dosing for ACTIMMUNE versus Proposed Clinical Dosing in This Study

	Approved ACTIMMUNE Dosing Regimen	Proposed ACTIMMUNE Dosing Regimen in Protocol HZNP-ACT-302
Age	All ages	10 to 25 years of age at start of HZNP-ACT-301
Route of administration	SC	SC
Individual dose	Per m^2 (or /kg if $<0.5 \text{ m}^2$)	Per m^2 (or /kg if $<0.5 \text{ m}^2$)
Maximum daily dose	$50 \mu\text{g}/\text{m}^2$ or $1.5 \mu\text{g}/\text{kg}$	$100 \mu\text{g}/\text{m}^2$ or $3 \mu\text{g}/\text{kg}$
Initial dose	No titration	Titration weekly from $10 \mu\text{g}/\text{m}^2$ to 25 , 50 , and $100 \mu\text{g}/\text{m}^2$
Frequency	TIW	TIW

There are several well-documented Investigational New Drug (IND)-reported, randomized, controlled clinical trials providing experience in large, late-stage subject populations such as liver disease (fibrosis) and idiopathic pulmonary fibrosis (IPF) at doses, frequency, and duration equivalent to those proposed for this study (i.e., 200 µg SC or approximately 100 µg/m²; Sponsor data on file). There are also reports from Europe on the use of higher doses of IFN- γ 1b in the treatment of FA [<https://fafysio.wordpress.com/>]. The clinical safety and tolerability at the 200 µg SC dose TIW appeared consistent with the safety described in the current package insert ([Section 17.2](#)).

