9.5.3.1.3 Grading of Adverse Events

The severity of all AEs, including all treatment-emergent clinically significant laboratory test results and all treatment-emergent clinically significant changes in laboratory test results, will be assessed in accordance with the following criteria:

- Mild (Grade 1): awareness of signs or symptoms that are easily tolerated, are of minor irritant type, cause no loss of time from usual activities, do not require medication or further medical evaluation, and/or are transient.
- Moderate (Grade 2): signs or symptoms sufficient to interfere with function but not activities of daily living.
- Severe (Grade 3): signs or symptoms sufficient to interfere with activities of daily living; signs and symptoms may be of a systemic nature or may require further medical evaluation and/or treatment.
- Life-Threatening (Grade 4): disabling or with life-threatening consequences. This definition does not include any event that might have caused death if it had occurred in a more severe form.
- Fatal (Grade 5): death related to an AE.

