9.5.3.1.5 Reporting and Documenting SAEs

All SAEs beginning with the time of signing IC and continuing until two weeks after administration of the final dose of study medication must be reported. The following steps will be taken to report promptly and document accurately any SAE, whether or not it appears to be related to the study medication:

- 1) Report the SAE to Med Communications, Inc. **by telephone or fax within 24 hours** after becoming aware that a subject has experienced an SAE (see [Appendix 17.1](#) for contact information).
- 2) Record the SAE accurately in the source documents and on the AE page of the subject's eCRF, as described in [Section 9.5.3.1.2](#). Using the Serious Adverse Event Reporting Form, submit all known subject information to Med Communications, Inc. (as specified in separate instructions provided to the study center) on the SAE reporting form **within 24 hours of learning of the SAE occurrence**.

- 3) Perform appropriate diagnostic tests and therapeutic measures, and submit all follow-up substantiating data, such as diagnostic test reports, hospital discharge summaries, and autopsy report to the Sponsor's representative.
- 4) Respond in a timely manner to any queries from Sponsor regarding the SAE.
- 5) Conduct appropriate consultation and follow-up evaluation until the SAE is resolved, stabilized, or otherwise explained by the Investigator.
- 6) Review each SAE report and evaluate the relationship of the SAE to study treatment. The Sponsor will determine whether the SAE is unexpected in nature.
- 7) The Investigator must report all AEs or SAEs that meet the criteria for Unanticipated Problems Involving Risks to Human Subjects or Others to the IRB.

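### The severe-reaction dosing rule makes no exception for acute serious hypersensitivity, and nothing in the protocol body requires a permanent stop

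*Protocol*

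**What the plan says.** Protocol 9.4.1.1 covers severe reactions during escalation, as judged by the investigator. The dose goes back to the previous level, or it "will be interrupted until the adverse reaction resolves and then restarted at the previous or a lower dose level". Once that level is tolerated, the dose may be raised again. The synopsis (Dose Regimen) carries the same two courses. So does 7.3, where "therapy will be interrupted until the adverse reaction resolves and then restarted at the previous or lower dose level". After Week 13 the dose cannot go up, and the only change that 9.4.1.1 names is that "it may be reduced on a case-by-case basis to manage subsequent drug-related AEs".

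Section 17.2 reproduces the US label. Label section 5.5 and the label Highlights call for stopping the drug, with appropriate treatment, when an acute serious hypersensitivity reaction occurs; 5.5 says to stop immediately. Label section 4 contraindicates the drug both in patients with known hypersensitivity and in patients who develop it.

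Protocol 9.3.3 allows the investigator to end a subject's participation at any time. Its list of discontinuation reasons includes an adverse event that carries unacceptable risk.

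**The concern.** Both courses in the severe-reaction sentence put the subject back on drug. For most interferon reactions, such as flu-like symptoms or raised transaminases, that is sensible. For acute serious hypersensitivity it is the opposite of what the protocol's own appendix instructs. A site that follows the dosing section literally would resume a drug that the label then contraindicates.

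Some subjects will be new to the drug. Those who had placebo in HZNP-ACT-301 receive their first active dose in this study, at home at bedtime. The exclusion criterion in 9.3.2 rests on investigator opinion and does not mention hypersensitivity. Re-exposure after such a reaction could do serious harm, although the event is expected to be rare.

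**Working it through.** There is no planned figure to reproduce: the sample size has no statistical basis and the point concerns text. The check sets the relevant provisions side by side.

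1. **Same event, two instructions.** Take a severe acute hypersensitivity reaction in Week 3. Under 9.4.1.1 the subject is reduced, or paused and restarted, and may then be titrated up. Under label 5.5 the drug stops at once. Under label 4 it is then contraindicated. The two cannot both be followed.

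2. **Statements of the rule.** Synopsis, 7.3 and 9.4.1.1 = 3 statements, each with 2 outcomes; outcomes that end treatment = 0. This count describes one sentence, not all the dosing text. Five other places say the dose may be held for tolerability: synopsis Study Design, the synopsis schematic footnote, the Schedule of Assessments footnote, 9.1 and the Figure 9.1 footnote. SAP Section 3 repeats this. Holding does not imply a restart, but it is not a permanent stop either.

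3. **Is the label made binding?** The body cites Section 17.2 in 7.1 (1), 7.3 (3) and 9.2 (1): 1 + 3 + 1 = 5 citations. They serve approval status (the drug "is approved for use in the US in patients with CGD and SMO (see prescribing information in Section 17.2"), the safety profile, the recommended dose, safety at 200 µg, and flu-like symptoms. Citations that direct a stop = 0. The word hypersensitivity does not occur in the protocol body as supplied, only in the label.

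4. **Other stopping provisions.** The wording of 9.3.3 is permissive, and its adverse-event entry is a reason category for the case report form. Where the protocol wants a binding condition it writes one: withdrawal for pregnancy (9.5.3.2), and a stable tolerated dose by Week 13 in order to continue. Neither addresses an acute reaction.

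5. **Reach of the rule.** Section 9.5.3.1.3 separates "Severe (Grade 3): signs or symptoms sufficient to interfere with activities of daily living" from "Life-Threatening (Grade 4): disabling or with life-threatening consequences", and 9.4.1.1 does not tie severe reactions to that scale. If Grade 4 is included, the instruction is to reduce or restart. If it is excluded, 9.4.1.1 has no escalation-period instruction for it. The gap is clearest for a Grade 3 reaction that is also serious.

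6. **How permanent is the label's stop?** The dosing part of the label Highlights uses discontinuation in a temporary sense, until the reaction abates. So 5.5 alone does not establish permanence; that rests on label section 4. Label 5.5 describes interruption for transient rashes, which fits the protocol's rule, so rashes are outside this point.

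7. **Size.** The label gives no rate. Assumed range: 0 to a few subjects.

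**The case against.** The best defence is that 9.4.1.1 is a tolerability guide for subjects who continue, and that stopping belongs in 9.3.3, where an acute serious hypersensitivity reaction plainly fits the unacceptable-risk reason. The trigger is the investigator's opinion, restart requires resolution, and re-titration is optional. The label's own general rule (2.3) is equally broad, and a reader can let its specific sections prevail. Protocol Section 12 binds the investigator to high standards of medical practice. Serious events must be reported "within 24 hours of learning of the SAE occurrence", and sites must "Perform appropriate diagnostic tests and therapeutic measures"; medical-monitor review (9.5.3.1.8) and the DSMB (9.2) also apply. The Investigator Brochure and the separate dosing instructions, which are not available here, may already contain a stop.

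Most of this stands and limits the weight of the point. It does not remove the conflict. Section 9.3.3 permits a stop without requiring it, and Section 12 names no action. The label pairs its general rule with sections 4 and 5.5, whereas the protocol body carries over a general rule without either. The protocol also departs from the label on dose and titration by design, so a site cannot assume that the label governs wherever the two differ.

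A reader might infer that the protocol forces re-challenge after anaphylaxis, or that it leaves no way to stop. The documents do not support that: doses may be held, and the investigator may end participation at any time.

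**Conclusion.** The point holds as a minor safety correction. Read literally, the severe-reaction sentence prescribes resumed dosing for an event in which the appended label calls for an immediate stop and thereafter contraindicates the drug, and no body text makes a permanent stop mandatory. That goes beyond missing detail, because the stated rule points the wrong way for this event. The practical risk is nevertheless small: few cases are expected and several safeguards apply. No endpoint or analysis is affected. The conclusion assumes that the supplied protocol body is complete on this matter, and that any stop in the Brochure or the dosing instructions cannot be relied on unseen.

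**What to change.** In 9.4.1.1, with matching text in the synopsis and 7.3, add to the severe-reaction sentence:

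*except acute serious hypersensitivity reactions, at any time during treatment, for which study drug is permanently discontinued (Section 17.2, label sections 4 and 5.5; see 9.3.3).*

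In 9.3.3, list this as a mandatory treatment-discontinuation criterion, separate from the reason categories. Leave transient rashes under the existing interrupt rule. The phrase covering any time during treatment also closes the gap after Week 13.

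Cost: a short protocol amendment, which 9.7 sends through IRB approval, and a site letter. It adds no visits, procedures or subjects. The one downside is that a rare subject loses the option of re-challenge.
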